#### 1.1.9.4 Population level summary

See sections 1.1.9.5, 1.1.9.6 and 1.1.9.7.

#### 1.1.9.5 Primary estimand for the primary endpoint

Variable: Annualised rate of clinically relevant asthma exacerbations.

**Population level summary**: The inter-treatment ratio of rates of clinically relevant asthma exacerbations calculated as the number of exacerbation events per subject year during the efficacy evaluation period (period 4), between treatments with HDM SLIT-tablet and placebo.

Type of document	Date:	11-Aug-2022	
Document ID	Version:	4.0	
	Status:	Final	
INTERNAL USE	Page:	19 of 79	

**Intercurrent events (discontinuations) in period 4:** Period 4 begins on September 1st after treatment initiation for all subjects and lasts until the end of trial or discontinuation of treatment.

All subjects with observations in period 4 will be included in the analysis.

### 1.1.9.6 Secondary estimand for the primary endpoint

Variable: Annualised rate of clinically relevant asthma exacerbations.

**Population level summary**: The ratio of rates of clinically relevant asthma exacerbations calculated as the number of exacerbation events per subject year during the efficacy evaluation period (period 4) between treatments with HDM SLIT-tablet and placebo.

**Intercurrent events (discontinuations) in period 4:** For this estimand period 4 is defined to begin on September 1st for all subjects and last until the end of trial. Thus, discontinuation of treatment during period 4 is no longer captured through the definition of the primary endpoint. This means that if a subject discontinues trial treatment during period 4, no period 4 data will contribute to the analysis.

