2.5 Primary endpoint

The primary endpoint of the trial is the annualised rate of clinically relevant asthma exacerbations calculated as the number per year per subject during the efficacy evaluation period (period 4).

A clinically relevant asthma exacerbation must be medically confirmed and is defined as asthma worsening leading to at least one of the following criteria:

due to asthma, requiring systemic corticosteroids or d) Hospitalisation for more than 12 hours due to asthma, requiring treatment with systemic corticosteroids.

³⁹ A severe asthma exacerbation is defined as at least one of the following: a) Systemic corticosteroids for treatment of asthma symptoms for at least 3 days, or b) Emergency room visit due to asthma, requiring systemic corticosteroids, or c) Hospitalisation for more than 12 hours due to asthma, requiring treatment with systemic corticosteroids.

- Doubling of ICS dose compared to background treatment
- Systemic corticosteroids for treatment of asthma symptoms for at least 3 days
- Emergency room visit due to asthma, requiring systemic corticosteroids
- Hospitalisation for more than 12 hours due to asthma, requiring treatment with systemic corticosteroids

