Period 2 is the baseline period of 3 weeks following screening. For cohort 1, the baseline period is during Q1 - Q2 2018. For cohort 2, the baseline period is during Q4 2018 - Q2 2019. For cohort 3, the baseline period is during Q4 2019 - Q2 2020. For cohort 4, the baseline period will occur during Q4 2021 – Q2 2022. During the baseline period, eligible subjects or their parent/caregiver will fill in their asthma and rhinoconjunctivitis symptoms and medication use in an eDiary. Subjects will continue with their regular asthma background treatment. The subjects' regular asthma rescue mediation and rhinoconjunctivitis rescue medication must be replaced with the rescue medication provided by ALK at visit 2 with the exception of additional sponsor provided ICS, which is optional.

Period 3 is the treatment initiation and maintenance period to allow the treatment with the HDM SLIT-tablet to take effect. It starts at randomisation and lasts for at least 4 months. The period ends on 1 September 2018 for cohort 1, on 1 September 2019 for cohort 2, on 1 September 2020 for cohort 3 and on 1 September 2022 for cohort 4.

During the first 28 days of period 3, prespecified symptoms⁴⁰ occurring after IMP intake will be recorded by the subject/parent/caregiver in the eDiary. The reported symptoms will be evaluated by investigator and reported in the eCRF as solicited AEs.

Period 4 is the efficacy assessment period. Period 4 lasts until the end of trial or discontinuation from the IMP⁴¹ and during this period the rate of clinically relevant asthma exacerbations will be

⁴⁰ AEs identified by the World Allergy Organization (WAO) as local side effects of SLIT (Passalacqua et al. 2013).

⁴¹ Subjects will be discontinued from the IMP treatment after 2 severe asthma exacerbations in 12 consecutive months or 1 hospitalisation due to asthma requiring treatment with systemic corticoteroids.

evaluated from 1 September 2018 to 30 April 2020 (cohort 1), 1 September 2019 to 30 April 2021 (cohort 2), 1 September 2020 to 30 April 2022 (cohort 3) and 1 September 2022 to 30 April 2024 (cohort 4).

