5.1 Discontinuation from IMP treatment

Subjects must be discontinued from IMP treatment and should continue in the trial for safety assessments only under the following circumstances:

- If the subject experiences 2 severe asthma exacerbations within a 12 consecutive months period
- If the subject is hospitalised due to asthma requiring treatment with systemic corticosteroids
- The subject experiences severe or persistent symptoms of oesophagitis
- If the subject becomes pregnant
- If, in the investigator's opinion, continuation with IMP treatment would be detrimental to the subject's well-being

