8.3 Rescue medication

All rescue medication in this trial will be provided by ALK except adrenaline/epinephrine autoinjector. For ICS, subjects can choose to utilise their current background medication during exacerbations rather than using sponsor provided ICS.

The asthma and rhinoconjunctivitis rescue medication will be dispensed at the baseline visit. If needed, nebuliser or spacer will be re-imbursed by ALK. The rescue medication will be re-supplied as described in the Flowchart (Table 1) when needed.

Asthma rescue medication

- Salbutamol, inhaler 100 µg/dose
- Prednisolone or Prednisone tablets, 5 mg
- Budesonide, inhaler 100 µg/dose and/or 200 µg/dose
- Fluticasone propionate inhaler 50 µg/dose

The above generic names of rescue medication are the International Nonproprietary Names. Synonymous generic names may be used in local labelling.

For the inhalers, the strength and dosage may be stated differently in local labelling; nominal dosage or the dosage as being delivered by the device. For example, the nominal strength for Fluticasone propionate, 50 μ g/dose, may be labelled as 44 μ g delivered per actuation.

The rescue medication should be used in accordance with the product's labelling (e.g. SmPC or USPI).

The Salbutamol inhaler should be used when necessary according to the dosage instruction for Salbutamol inhaler: Up to 2 doses 4 times per day.

Prednisolone/Prednisone tablets may only be used under the supervision of the investigator or designee. The dosing should be in accordance with the product's labelling for the treatment of an asthma exacerbation and the dosing recommendations by **GINA Executive Committee**

2017, NIH guidelines (National Heart Lung and Blood Institute 2007) or national guidelines (Reddel et al. 2009).

For children, the dosing of prednisolone/prednisone is typically 1-2 mg/kg body weight divided into 1-2 doses daily for 3-5 days.

The doubling of ICS, either by using a Budesonide or Fluticasone propionate inhaler, based on equipotency of the corticosteroids, or by using the subject's own background medication, should only be used under the supervision of the investigator or designee. Doubling of ICS is not permitted for subjects on high dose ICS.

Rhinoconjunctivitis rescue medication

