#### 1.1.9.3 Intercurrent events

Discontinuation of treatment, both before and during the efficacy period, is considered an intercurrent event and will be handled by the hypothetical strategy.

Different approaches for discontinuation of treatment during the efficacy period are applied for the primary and the secondary estimands (see sections **1.1.9.5**, **1.1.9.6** and **1.1.9.7**.). The difference between the primary and the secondary estimands for the primary endpoint is the inclusion or exclusion of data from subjects who discontinue treatment during period 4, respectively.

If a subject discontinues treatment prior to the efficacy period (period 4 for the primary endpoint and visit 5 to visit 11 for the key secondary endpoints), no data from the efficacy period will contribute to the analysis of the primary and secondary estimands.

As only 3 subjects discontinued treatment but did not withdraw from the trial at the time of treatment discontinuation, the discontinuation of trial is not considered with respect to the intercurrent events as it will not add information to make a separate analysis approach (treatment policy estimand) for these very few subjects.

In allergy immunotherapy clinical trials, rescue medication is dispensed to every subject. Therefore, rescue medication is expected to be used as part of the trial design, and hence use of rescue medication is not classified as an intercurrent event.

As all estimands follow the hypothetical strategy, they assess the anticipated effect of the trial product if taken as instructed.

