### 3 ANALYSIS SETS

For the purposes of analysis, the following participant analysis sets are defined:

Analysis set	Description
FAS	The FAS consists of all randomised subjects, who received at least 1 dose of IMP. Subjects will be analysed as randomised, i.e. according to their randomised assignment of treatment.
SAF	The SAF consists of all randomised subjects, who received at least 1 dose of IMP. Subjects will be analysed as treated, i.e. according to the treatment they actually received.
PP	The PP will consist of all subjects in FAS without protocol deviations, which may substantially affect the primary endpoint. Subjects will be analysed as randomised, i.e. according to their randomised assignment of treatment.

Before database lock, a list will be made that defines which subjects in FAS are not included in PP and the reason for this. The criteria for not including subjects in PP are the following:

- 1. Violation of the inclusion/exclusion criteria that may potentially impact the primary endpoint
- 2. Use of prohibited medication close to or during the efficacy evaluation period (period 4) that may potentially impact the primary endpoint
- 3. Treatment compliance in the entire trial. Subjects with a treatment compliance below 80% are not included in the PP
- 4. Efficacy compliance. Subjects with less than 6 months of efficacy assessment in period 4 are not included in the PP

The list of subjects in PP is found in Appendix 4 section 7.4.

The FAS will be used for baseline tables and efficacy output and the SAF will be used for safety tables and listings. The PP will be used for a supportive analysis of the primary endpoint.

DPS	Description
DPS1	
 
Subjects who are treated in period 4 will be included.
 
Post-discontinuation data will not be included.
 

DPS2	
 
Only subjects who complete treatment in period 4 will be included.
 

The following data point sets are defined:

FAS and DPS1 are used to estimate the primary estimand for the primary endpoint and the primary estimand for the key secondary endpoints.

FAS and DPS2 are used to estimate the secondary estimand for the primary endpoint.

Type of document	Date:	11-Aug-2022	
Document ID	Version:	4.0	
	Status:	Final	
INTERNAL USE	Page:	28 of 79	

In addition, to investigate the impact of covid-19 (see section **3.2**), the following observation periods are defined:

OP	Description

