# 7 SUPPORTING DOCUMENTATION

# 7.1 Appendix 1: Definitions and derivations

#### 7.1.1 Derivation of endpoints from eCRF data

#### 7.1.1.1 Clinically relevant and severe asthma exacerbation endpoints

The source for deriving the clinically relevant asthma exacerbation and the severe asthma exacerbation endpoints is the AE form of the eCRF. On the AE form the clinically relevant asthma exacerbations are reported with an AE number, a start and a stop time/date and the criterion/criteria fulfilled for the event being categorised as a clinically relevant or severe asthma exacerbation. If at least 1 of the 4 criteria listed in section **1.1.5** is fulfilled, the event is considered a clinically relevant asthma exacerbation. If at least 1 of the 4 criteria listed in section **1.1.5** is fulfilled, the event is considered a clinically relevant asthma exacerbation. If at least 1 of last 3 criteria listed in section **1.1.5** is fulfilled, the event is additionally considered to be a severe asthma exacerbation.

A clinically relevant asthma exacerbation must be separated by more than 7 days from a previous clinically relevant asthma exacerbation in order to be considered an individual event, i.e. the difference between the start date of an event (i) and the stop date for the previous event/events (i-1) must be more than 7 days:

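### The completers-only secondary estimand (DPS2) selects subjects partly on the primary outcome, so its ratio is not the effect under treatment as instructed (minor, non-confirmatory)

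*SAP*

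**What the plan says.** SAP 1.1.9.6 defines the secondary estimand of the primary endpoint so that "if a subject discontinues trial treatment during period 4, no period 4 data will contribute to the analysis". SAP section 3 implements this as DPS2: "Only subjects who complete treatment in period 4 will be included". Table 1 runs it as a negative binomial regression on FAS/DPS2, with and without a Covid-19 effect (4.2.6).

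Protocol 5.1 lists five reasons why treatment must stop. Two are exacerbation rules. One is "If the subject experiences 2 severe asthma exacerbations within a 12 consecutive months period"; the other is an asthma hospitalisation requiring systemic corticosteroids. Footnote 41 in protocol 3.1 attaches both to the sentence that ends period 4 at treatment discontinuation: "Subjects will be discontinued from the IMP treatment after 2 severe asthma exacerbations in 12 consecutive months or 1 hospitalisation due to asthma".

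SAP 7.1.1.1 makes severe exacerbations a subset of primary-endpoint events: when any of the last three of the four endpoint criteria is met, "the event is additionally considered to be a severe asthma exacerbation".

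SAP 1.1.9.3 concludes: "As all estimands follow the hypothetical strategy, they assess the anticipated effect of the trial product if taken as instructed".

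**The concern.** A subject stopped under either exacerbation rule in period 4 leaves DPS2, and the on-treatment events already recorded leave too. Whether a subject is analysed therefore depends partly on how many primary-endpoint events that subject had. Completers selected in this way do not show what would have happened had everyone stayed on treatment.

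If the drug works, more high-event subjects are expected to be removed from placebo than from active, which pulls the ratio toward 1. A weaker result in the secondary-estimand row, or in its Covid-19 version, could then be read as a lack of robustness or as the effect in adherent subjects. It would be neither.

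**Working it through.** **How tight the link is.** If the stop rules are followed, no DPS2 subject can have two severe exacerbations within 12 months or a hospitalisation that meets the rule. The link is tightest on high-dose ICS. Protocol 8.3 states: "Doubling of ICS is not permitted for subjects on high dose ICS". Every endpoint event these subjects can have is therefore severe, and DPS2 allows them at most two in 20 months, more than 12 months apart.

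The link is not complete, in two ways. The endpoint criterion is "Hospitalisation for more than 12 hours due to asthma, requiring treatment with systemic corticosteroids", but the stop rule has no 12-hour minimum, so a shorter stay forces a stop and counts only if another criterion is met. Events in period 3 can also use up the 12-month window without counting.

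**Whether the SAP covers it.** The missing-completely-at-random statement in 4.2.3 is explained only for discontinuation before period 4. Both sensitivity analyses in 4.2.4 challenge the primary estimand. No assumption is stated for period-4 stops under DPS2.

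**The plan's own figure.** With z = 1.2816 + 1.9600, a 30% reduction, μ1 = 2.293, μ2 = 1.605 and k = 0.7, the closed formula gives N = 82.59 × (1.059 + 1.4) = 203 per arm, against 202 in SAP Table 5.

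**Mechanism at the planning inputs** (1.4 per year, k = 0.7, true ratio 0.70; assumed 5% of severe events hospitalised and 15% outcome-independent drop-out). With half of events severe, forced stops take about 27% of placebo and 18% of active subjects. The completers' placebo rate falls to 0.75 per year, and DPS2 gives 0.80 while DPS1 gives 0.70. With the stop rule switched off, DPS2 returns 0.70.

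**More realistic rates.** SAP 5.1 reports 81% power at 900 subjects but not the inputs. I solved the reassessment formula in protocol 15.2.1 for the rate, with 450 per arm, ratio 0.70, and assumed 5% drop-out and 584 days (1.6 years):

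- {(0.878 + 1.960)/ln(1/0.7)}² = 63.3
- 450 × 0.95/63.3 = 6.753 = 2.89/(2 × μ_total × 1.6 × 0.7) + 2k
- k = 0.7: μ_total = 1.290/5.353 = 0.241, and placebo = 0.241/0.85 = 0.284 per year
- k = 1.5 (assumed): 0.404. k = 2.0 (assumed): 0.551.

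Drop-out of 2–10% and 550–608 days give 0.26–0.32, 0.37–0.47 and 0.49–0.67.

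**Simulation.** Gamma-Poisson event times over 608 days, with or without a preceding 122–304 days of period 3; forced stop at the second severe event within 365 days or the first hospitalised severe event; 8% other stops (assumed). The base is 533 − 9 (site 613) = 524 subjects. The true ratio is 0.70. Assumed: 25–50% of events severe, 5–10% of severe events hospitalised.

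| k (placebo rate) | DPS2, period 4 only | DPS2, period 3 counts toward the rule | Forced stops of 524 (period 3 counted) | DPS2, rates halved for Covid-19 | DPS1, period 3 included |
|---|---|---|---|---|---|
| 0.7 (0.28) | 0.709–0.731 | 0.712–0.735 | 6–21 | 0.705–0.722 | 0.692–0.700 |
| 1.5 (0.40) | 0.726–0.767 | 0.732–0.778 | 12–35 | 0.715–0.741 | 0.702–0.706 |
| 2.0 (0.55) | 0.743–0.803 | 0.760–0.824 | 20–48 | 0.731–0.770 | 0.715–0.733 |

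The halved-rate column includes period 3 and uses 5% hospitalised.

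- **Few forced stops** (severe share 5–15%, about 1–3 stops): DPS2 is 0.703–0.710.
- **Events dropped at k = 0.7:** 7–22 placebo and 4–13 active on-treatment events, through forced stops.
- **High-dose ICS alone** (all events severe, overall rate applied, period 3 included): 0.81, 0.86 and 0.90. Without period 3: 0.79, 0.84 and 0.88. The size of this group is not given.
- **No drug effect:** 0.997–1.005 when other stops are independent of risk, even at 4% versus 12%. If other stops are both unequal (4% versus 12%) and proportional to risk, 0.948–1.052 at k = 0.7 and 0.906–1.113 at k = 2.0.

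Seasonality and the merging of events 7 days or less apart were not modelled.

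**The case against.** **It is openly a completers analysis.** SAP 1.1.9.3, 1.1.9.6, section 3 and Table 1 all say that discontinuers are excluded, and the primary row stands beside it. That is true, and it limits the criticism to the estimand label and one over-broad sentence.

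**Few subjects may be affected.** SAP 1.1.9.3 says only 3 subjects stopped treatment without leaving the trial at that time, while protocol 5.1 says force-stopped subjects should stay. This points to the low end of the range. It is not an upper bound, because protocol 9.4 lets permanent stoppers leave the trial. The larger scenarios require many of them to have done so, and should not be read as expected.

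**DPS1 is not exact either.** At k = 2.0 with period-3 history it gives 0.715–0.733. This is as far from 0.70 as DPS2 is at k = 0.7. Within the same k, DPS2 is clearly further off.

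**The remedy is partly a choice.** A biased estimator does not invalidate a hypothetical target. The sponsor could instead keep the estimand and state the assumption it needs, or estimate it from data up to the stop, as DPS1 does. Either would also remove the contradiction.

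**Conclusion.** The concern holds and is minor. Protocol 5.1 and the DPS2 definition together make inclusion depend partly on the primary outcome, so the statement in SAP 1.1.9.3 is wrong for DPS2 whatever the number of forced stops.

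For a true ratio of 0.70, the shift toward 1 ranges from at most about 0.01 (one to three forced stops) to about 0.01–0.04 at k = 0.7 and up to about 0.12 at k = 2.0. The larger figures rest on assumed severe shares, hospitalised shares and dispersions that the documents do not give. The confirmatory test uses the primary estimand (SAP 2.1) and is not affected.

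**What to change.** 1. In SAP 1.1.9.6, section 3 and Table 1, and for the Covid-19 version in 4.2.6, relabel DPS2 as a descriptive completers analysis. State that completion depends on the endpoint through protocol 5.1.
2. Limit the closing sentence of SAP 1.1.9.3 to the DPS1-based estimands.
3. Report by arm the number of subjects stopped under the two exacerbation rules, and the on-treatment period-4 events that DPS2 drops. The planned tables come close (primary reason for discontinuation in 6.1; asthma-related symptoms leading to discontinuation in 4.5.2), but they neither name the two rules nor count the dropped events.

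The cost is a little wording, one relabelled table row and two counts per arm. No new data are needed, and neither the primary analysis nor any clinical rule changes.

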### 1.1.9.7 Primary estimand for the key secondary endpoints

Variable: Each key secondary endpoint defines a variable for the estimand.

**Population level summary**: The absolute difference in means of the endpoint between treatment with HDM SLIT-tablet and placebo or the ratio between treatment means of the endpoint between treatment with HDM SLIT-tablet and placebo (depends on the definition of each endpoint).

**Intercurrent events (discontinuations) in efficacy period:** Discontinuations in the efficacy period will be handled as for the primary estimand for the primary endpoint. The efficacy period for the key secondary endpoints is defined as visit 5 – visit 11.

### 1.2 Trial design

This trial is a randomised, parallel-group, double-blind, placebo-controlled, multi-national phase III trial conducted in Europe and North America.

The trial was initiated in Q1 2018 and subjects were to receive treatment for 24-30 months consisting of a treatment initiation and maintenance period of 4-10 months followed by a 20-month efficacy assessment period.

A total of 533 subjects were randomised to receive treatment with the HDM SLIT-tablet or placebo, see **Figure 1**.

Type of document Document ID	Date: Version: Status:	11-Aug-2022 4.0 Final	
INTERNAL USE	Page:	20 of 79	

#### 12 SQ-HDM, 300 subjects N = 600 Placebo, 300 subjects Period 3 Period 2 Treatment Period 4 Period 1 initiation and Screening 3 weeks Baseline; Efficacy assessment period; maintenance; 20 months 4-10 months Screening visit Randomisation Baseline visit End of trial visit Å Solicited /isit /isit ٧9 ٧1 V2 V4 V6 ٧7 ٧8 V10 V11 V3 ٧5 3 weeks 4 weeks 3 months 4 months 4 months 4 months 4 months 4 months

### Figure 1 Overview of trial design

Period 1 is the screening period.

Period 2 is the 3-week baseline period during which eligible subjects will fill in their asthma and rhinoconjunctivitis symptoms and medication use in an electronic diary (eDiary). Only the 2 last weeks of the 3-week baseline period will be used for calculation of baseline scores. At the start of period 2 (visit 2) subjects' regular asthma rescue mediation and rhinoconjunctivitis rescue medication will be replaced with the rescue medication provided by ALK.

Period 3 is the treatment initiation and maintenance period to allow the treatment with the HDM SLIT-tablet to take effect. It starts at randomisation and lasts for 4-10 months. Period 3 ends the 31st of August. During the first 28 days of period 3, 15 prespecified symptoms occurring after IMP intake will be assessed by the subject/parent/caregiver in the eDiary. The reported symptoms will be evaluated by investigator and reported, based on the investigator's medical evaluation and discretion, in the eCRF as solicited AEs.

Period 4 is the efficacy assessment period for the primary endpoint. Period 4 begins on September 1st for all subjects and lasts until the end of trial or discontinuation from IMP. During this period, the rate of clinically relevant asthma exacerbations will be evaluated.

Every 4 months after randomisation, subjects or their parent/caregiver will be asked to complete the eDlary for a period of 14 days 3 weeks prior to V5 (at 4 months), V6 (at 8 months), V7 (at 12 months), V8 (at 16 months), V9 (at 20 months), V10 (at 24 months) and V11 (25-29 months).

